Insomnia disorder is defined as persistent difficulties with sleep initiation and/or maintenance, resulting in significant daytime impairment. Insomnia affects approximately 10–12% of the adult population and is associated with increased risk for cardiovascular disease, depression, and early mortality (Morin et al., 2015; Morin and Benca, 2012). Maladaptive emotion regulation strategies, such as worry and rumination, are prominent features of both insomnia disorder and depression (Carney et al., 2010; Liu and Thompson, 2017). While these maladaptive strategies confer risk for depression (Wilkinson et al., 2013), recent data show that they also mediate the relationship between poor sleep quality and depressive symptoms in both longitudinal (O'Leary et al., 2017) and cross-sectional (Hom et al., 2016) analyses. Experimental laboratory studies have shown that sleep restriction in healthy participants results in decreased ability to down-regulate emotions in response to emotional stimuli (Mauss et al., 2013; Reddy et al., 2017; Tamm, Sandra et al., 2019) and sleep deprivation engenders impairments in emotion perception, attention and memory, as well as alterations in the neurophysiological structures sub-serving these functions (Krause et al., 2017). However, whether treatment of insomnia with cognitive behavioural therapy (CBT) leads to improved emotional processing is not known.

Aim and hypotheses

The aim of the present study is to test if digital cognitive behaviour therapy for insomnia (dCBT-I) modifies emotional processing, including both objective measures of affective bias and self-report measures of emotional regulation, worry, perseverative negative thinking, mood and chronotype in patients with insomnia and comorbid depressive symptoms. Furthermore, it aims to examine if changes in emotional bias and/or emotional regulation mediate the effect of CBT-I on depressive symptoms.

The **primary hypothesis** for the trial is:

- 1. dCBT-I will improve objective biases in negative emotional processing of faces relative to Sleep Hygiene Education (SHE) (10 weeks post randomisation)
- a. Reduced recognition accuracy in response to sad facial expressions in the Facial Emotional Recognition Task (FERT)
 - b. Increased recognition accuracy in response to happy facial expressions in the FERT

The **secondary hypotheses** are:

- 1. dCBT-I will improve objective biases in negative emotional processing of faces relative to Sleep Hygiene Education (SHE) (5 weeks post randomisation)
- 2. dCBT-I will improve objective negative biases in categorization of emotional self-descriptors (5 and 10 weeks post randomisation) relative to SHE
- a. Decreased reaction time to identify positive compared with negative characteristics in Emotional Categorisation Task (ECAT)

- 3. dCBT-I will increase positive emotional memory bias relative to SHE (5 and 10 weeks post randomisation)
- a. Increased memory for positive compared with negative words in the Emotional Memory Task (EMEM)
- 4. dCBT-I will reduce self-reported emotion regulation deficits (Difficulty with Emotion Regulation Scale, DERS), worry (Penn State Worry Questionnaire, PSWQ) and perseverative thinking (Perseverative Thinking Questionnaire, PTQ) (5 and 10 weeks post randomisation) relative to SHE
- 5. dCBT-I will reduce self-reported depression severity (Patient Health Questionnaire, PHQ-9) (5 and 10 weeks post randomisation) relative to SHE
- 6. dCBT-I will reduce insomnia severity (Insomnia Severity Index, ISI) (5 and 10 weeks post randomisation) relative to SHE
- 7. Change in emotional perception of faces (FERT: Changes in recognition accuracy for happy and sad facial expressions) at week 5 will mediate change in depressive symptoms (PHQ-9) at week 10
- 8. Change in emotion processing (ECAT: reaction times for positive compared with negative words) at week 5 will mediate change in depressive symptoms (PHQ-9) at week 10.
- 9. Change in self-rated emotion regulation, worry and preservative thinking (reductions in DERS, PSWQ and PTQ scores) at week 5 will mediate the effect of dCBT-I over SHE on depressive symptoms (PHQ-9) at week 10
- 11. dCBT-I will increase the level of morningness (Munich ChronoType Questionnaire, MCTQ) (5 and 10 weeks post randomisation) relative to SHE
 - a. Earlier midpoint of sleep on work-free days, sleep-corrected (MSF SC)
- 10. dCBT-I will increase positive affect (Positive and Negative Affect Schedule Short Form Positive affect, PANAS-SF: PA) and reduce negative affect (Positive and Negative Affect Schedule Short Form Negative affect, PANAS-SF: NA) (5 and 10 weeks post randomisation) relative to SHE
- 12. Change in level of morningness (MSF SC from MCTQ) at week 5 will mediate change in depressive symptoms (Patient Health Questionnaire, PHQ-9) at week 10
- 13. Change in mood (PANAS-SF: PA and NA) at week 5 will mediate change in depressive symptoms (PHQ-9) at week 10

Method

Study design

The study is a parallel-group, superiority RCT of digital Cognitive Behavioural Therapy for Insomnia (dCBT-I) versus Sleep Hygiene Education (SHE) control. The study is carried out online and through phone contact with the study team. Participants are screened and provide informed consent online.

Assessments (tasks and questionnaires), allocation to condition, and intervention is carried out through web-based platforms. Online outcome assessment of our primary and secondary dependent variables take place at 0 (baseline), 5 weeks post-randomisation (mid-treatment) and 10 weeks post-randomisation (post-treatment). At week 10 all participants allocated to the SHE are offered dCBT-I to improve their insomnia. Participants are scheduled for a phone call before the baseline assessment to go

through the study procedures, and 2 weeks post randomization to ensure that they have accessed the treatments.

Inclusion/exclusion

We will recruit circa 200 community participants who report clinically-significant insomnia and depressive symptoms. Our inclusion criteria comprise of:

- A positive screen for probable DSM-5 insomnia disorder using items from the Sleep Condition Indicator (SCI) (scoring ≤ 2 on item 1 (sleep latency) or item 2 (wakefulness during the night) + scoring ≤ 2 on item 3 (frequency of disturbance) + scoring ≤ 1 on item 4 (sleep quality) + scoring ≤ 2 on daytime functioning items 5 or 6+scoring ≤ 2 on item 8 (chronicity of problem))
- Endorsement of depressive symptoms in the probable "caseness" range (PHQ score ≥10)
- Aged 25-65 years
- Access to a laptop or desktop computer and a phone and reliable internet access either at home or work
- Being able to read and understand English
- Currently living in the UK.

We will screen for comorbid conditions and medication use via an online survey and exclude people according to the following criteria:

- Engaged in psychotherapy for insomnia or depression
- Previous participation in online (or face to face) sleep treatments
- Hypnotic, psychotropic, or antiepileptic medications
- Psychiatric comorbidities: Psychosis or Bipolar Disorder
- Diagnosis of epilepsy or other neurological disorder
- Diagnoses of mild cognitive impairment or dementia.
- Symptoms of a probable additional sleep disorder (e.g. possible obstructive sleep apnea, restless legs syndrome)
- Serious physical health concerns necessitating surgery or with a survival prognosis of < 6 months
- Habitual night shift, evening, or rotating shift-workers (assessed during last month)
- Suicidal thoughts (Score >1 "yes" on C-SSRS suicide item 2), history of recent suicide attempt (<12 months)
- Psychiatric hospital admission in the past year, or crisis team support within the past year.
- Alcohol misuse & dependency or recreational/illicit drug use

Measurements

The primary and secondary outcome measures are collected at baseline, at 5 weeks and at 10 weeks. The 5 weeks assessment expires after 5 weeks (i.e. at the time of the last assessment) and the 10 weeks assessment expires 4 weeks after the scheduled date, and after the assessments expire participants are no longer able to complete the assessment. The following table lists the variables collected during the trial:

Type of	Measure	Pre-	Baseline	Mid-	Post-
variable		Study	(Week 0)	Treatment (Week 5)	Treatment (Week 10)
	Online Eligibility Screen	Х			
	Demographics		Х		
Primary	FERT		Х	Х	Х
outcome					
and					
mediator					
Secondary	Self-report Emotion		X	X	X
outcome	Regulation: DERS,				
and	PSWQ, PTQ				
mediator					
Secondary	Mood instability		X	X	X
outcome					
Secondary	ISI		X	X	X
outcome					
Secondary	PSQI (4 items)		Χ	X	Χ
outcome					
Secondary	Depression (PHQ-9)		X	X	X
outcome					
Secondary	Chronotype		Х	X	X
outcome					
and					
mediator	Danisius and		V		V
Secondary	Positive and		X	X	X
Outcome and	Negative Affect				
mediator					
Secondary	ECAT		X	X	X
outcome	EGAT		^	^	^
and					
mediator					
Secondary	EMEM		Χ	X	Χ
outcome			^		
and					
mediator					
Auditory	Audit of engagement			Х	Х
variable	with mental health				
	services and sleep				
	medication				
Auditory	Device Monitoring		Х	Х	Х
variable	Question(s)				

Randomisation and allocation concealment

Randomization will be performed independently from the study team through the ePRO system. This study will use stratified randomisation with an allocation ratio of 1:1. Randomisation and stratification according to sex (male/female), age (25-44, 45-65), depression severity (PHQ-9 Scores: $\leq 15: \geq 16$) and insomnia severity (ISI scores $\leq 19: \geq 20$). On completion of baseline measures each participant will be randomly assigned to either dCBT-I or SHE. The team will be unable to influence randomization in the ePRO system, but will manually contact the participant to inform them of their allocation.

Sample size calculation

Our planned primary intention-to-treat analysis will compare dCBT-I versus SHE for objective biases in negative emotional processing of faces at week 10. Our desired sample size of n=200 and an estimated attrition rate of 15% (based on recently completed trials (Kyle et al., 2017)), was powered to detect a minimum between group standardized effect size of 0.5 at week 10, with a power of 90% and a two-tailed α of 0.05.

Considering the co-primary outcome, alpha will be adjusted to 0.025 to control the overall type 1 error rate. Therefore, conservatively assuming an alpha of 0.025 and no correlation between the outcomes; the study would be able to detect an effect size of 0.5 with 85% power on the two primary outcomes (recognition accuracy in response to happy and sad facial expressions). The sample size remains inflated to allow for a rate of by 15% lost to follow up.

Adverse events

Since the trial is completed online, with limited formal participant contact, we are unlikely to become aware of all potential adverse events. However, should we do so, we will define serious adverse events as: (1) death, (2) suicide attempt, and (3) admissions to secure units.

[figure not shown]
Analysis – general considerations

Statistical software

Analyses and processing of the data will be performed in R (R Core Team (2020). R: A language and environment for statistical computing. R Foundation for Statistical Computing, Vienna, Austria. https://www.R-project.org/). Mixed effect models will be run using the lme4 and nlme packages, CACE analyses will be performed using the eefAnalytics package and mediation analyses will be performed using the MEDIATION package.

Descriptive statistics

We will present the data using a CONSORT diagram, see figure below.

Frequencies (with percentages) for binary and categorical variables and means (and standard deviations), or medians (with lower and upper quartiles) for continuous variables will be presented by intervention group as well as overall.

Characteristics of participants

Baseline variables will be presented by randomised group using frequencies (with percentages) for binary and categorical variables and means (and standard deviations) or medians (with lower and upper

quartiles) for continuous variables. There will be no tests of statistical significance nor confidence intervals for differences between groups on any baseline variables. Baseline characteristics will be presented by randomised group and overall.

Definition of population for analysis

The primary analysis population will include all participants randomised who have at least one outcome measurement. Participants who withdraw from the trial will be included in the analysis until the point at which they withdraw. Participants will be analysed according to their allocated treatment group irrespective of what treatment they actually receive.

Primary analysis

Primary outcome

Our primary outcome measure will be the Facial Expression Recognition Task [FERT]. The FERT assesses the interpretation of facial expressions (Harmer et al., 2009). Faces with six different basic emotions (happiness, fear, anger, disgust, sadness, surprise) are displayed on a screen and participants are required to indicate the expression on the face by selecting a corresponding button. The task takes approximately 15-20 minutes to complete and assesses the following dependent variables: Emotion Accuracy, Emotion Misclassifications, Emotion Reaction time, Target Sensitivity for each emotion and Response bias for each emotion. The primary outcomes for the study are accuracy for sad and happy facial expression and are defined as the percentage of accurately identified faces for each emotion (Number of correct responses for each emotion)/(Number of faces of each emotion). We will also report Emotion Misclassification and Emotion Reaction Time (see exploratory analyses, below).

The main efficacy analysis will be conducted on a modified intention-to-treat basis including all participants having at least one outcome. The primary analyses (emotional processing of faces) differences between treatment groups (dCBT-I and SHE), will be estimated with mixed linear regression models. The main objective of the statistical analyses is to assess the effect of dCBT-I on the primary outcome at the end of the intervention period, 10 weeks. To this end a linear mixed modelling will be employed. In such models, the continuous outcome variable measured at the post randomisation time points features as the dependent, the baseline value of the outcome, stratification factors (sex, age, depression severity and insomnia severity), treatment arm (dCBT-I or SHE), assessment time (5 or 10 weeks) and a treatment x time interaction term included as covariates. To account for correlation between repeated measures on the same individual a subject-varying random intercept will be included. Time will be considered as a categorical variable and model fitted assessed for inclusion of a random slope. Model assumptions will be checked using diagnostic plots. Modelling will be based on the assumption that data are missing at random and will be fitted using restricted maximum likelihood estimation. Results from all analyses will be summarised at 5 and 10 weeks with 2 sided 97.5 % CIs and we will present the data from both adjusted (including stratification variables) and unadjusted models. The adjusted model will be considered the primary analysis.

Handling missing data

The analysis will use statistical techniques for handling missing outcome data under a missing-at random assumption (MAR). The availability of the outcome data for the primary outcome at 10 weeks will be summarised by randomised group.

The mixed effects model implicitly accounts for data missing at random, however the data missingness mechanism will be explored. Logistic regression models will explore any association between baseline characteristics and availability of the primary outcome at 10 weeks. Missing primary outcome data will be reported overall and by randomised group. Covariates found to be predictive of missingness (P< 0.05) will be included in the analysis model in a sensitivity analysis of the primary outcome.

If post randomisation variables, such as compliance with treatment, or baseline variables are found to be predictive of non-completion of outcome, such that it would not be suitable to adjust for them in the main analyses, then multiple imputation will be considered.

Handling outliers

Any outliers will be checked and verified to ensure that they are true values. Outliers will be identified as those observations more than four standard deviations from the mean. Once they have been confirmed, a sensitivity analysis will be carried out to assess the impact of these values on the results by excluding these participants (see below).

Multiple comparisons and multiplicity

The primary outcome is clearly stated in the protocol. Due to the use of 2 primary outcomes (accuracy for sad and happy faces, respectively) 0.05/2 = 0.025 will be considered significant for the main analysis.

Model assumptions

Standard residual diagnostics, such as inspection of the histogram of the residuals, will be used to assess the appropriateness of the model. If assumptions are violated we will consider firstly using the change in accuracy from baseline as the dependent variable. If the assumptions are still violated we will consider alternative non- parametric approaches.

Secondary analysis

Secondary outcomes

Continuous secondary outcomes will be analysed in the same way as the primary outcome. We will test the hypothesis for between-group difference in the outcomes at 5 weeks and 10 weeks using mixed effects models with baseline outcome measure, treatment assignment, assessment time, stratification variables and a treatment by time interaction as fixed effects with a subject-varying random intercept. We will apply standard regression diagnostics. The proposed analysis assumes that these secondary outcomes are continuous and satisfy the assumptions of the mixed effects model. Where these assumptions are not satisfied, the data will be transformed or if a transformation is not possible, a non-parametric approach to analysing the data will be adopted.

The secondary outcomes include:

Self-rated

The Difficulties in Emotion Regulation Scale (DERS), total score

The Patient Health Questionnaire (PHQ9)

The Penn State Worry Questionnaire PSWQ-Past Week (The PSWQ-PW)

The Perseverative Thinking Questionnaire (PTQ)

Insomnia Severity Index (ISI)

Mood Instability (one self-rated item from the Structured Clinical Interview for DSM-IV (SCID-II))

Munich Chronotype Questionnaire (MCTQ)

Positive and Negative Affect Schedule – Short Form (PANAS-SF)

Objective task performance

Emotion accuracy from the Facial Expression Recognition Task [FERT, see above] at week 5 will be considered a secondary outcome.

Emotional Categorisation Task [ECAT]. The ECAT assesses speed to respond to positive and negative self-referent personality descriptors. Participants are asked whether they would like or dislike to be referred to as each characteristic. The task takes approximately 5 minutes to complete and generates the following dependent variables: % Accuracy of each condition (positive or negative words), % misses of each condition (positive or negative words) and mean reaction time for correct responses for each condition (positive or negative words). The mean reaction time for correct responses for positive vs negative words will be considered the main outcome for this task, but we will also report % accuracy and % of misses (see below).

Emotion Recognition Memory Task [EMEM]. The EMEM measures recognition memory for affective words. Participants are presented with a series of words comprising the pleasant and unpleasant personality words that were previously presented to them in the ECAT, and a set of previously unseen distracter words. For each word, participants are required to report whether they have previously seen the word. The task takes approximately 10 minutes to complete and % accuracy of positive compared to negative words will be considered the main outcome for the task. We will also report misclassifications of each condition (positive or negative words) and mean reaction time for correct responses for each condition (positive and negative words) (see below).

Treatment engagement

For participants in the CBT-I intervention arm the following information will be reported: Total number of completed sessions in Sleepio.

For participants in the sleep hygiene arm the following information will be reported: Number of unique IP addresses logging in to the bespoke Sleep Hygiene advice page.

Mediation analysis

The following variables will be investigated as possible mediators (at week 5) of the association between treatment group and depressive symptoms (at week 10):

Changes in recognition accuracy for happy and sad facial expressions (FERT)

Change in reaction times for positive compared with negative words (ECAT)

Change in self-rated emotion regulation, worry and preservative thinking (reductions in DERS, PSWQ and PTQ scores)

Change in level of morningness (MSF SC from MCTQ)

Change in mood (PANAS-SF, positive and negative affect)

If the efficacy analysis shows significant between-group differences in these measures at 5 and 10 weeks, modern causal inference methods will be used to investigate the mediation hypotheses. Parametric regression models will be employed to test for the indirect effect of emotion regulation/processing/morningness/mood at week 5 on depression severity (PHQ-9) at 10 weeks. Since all the measures are continuous, the indirect effects are calculated by multiplying relevant pathways and bootstrapping is used to produce valid standard errors for the indirect effects. Results will be presented as indirect effects with 95% bootstrapped percentile CIs and also as percentage of the total effect that is mediated. All analyses will adjust for baseline measures of the mediators. An adjusted model, including the stratification variables will also be presented. Mediation analyses are potentially biased by measurement error in mediators and hidden confounding between mediators and outcomes and we will investigate the sensitivity of the estimates to these problems.

CACE analysis

A complier-average causal effect (CACE) analysis of the primary outcome will be carried out to determine what effect the level of compliance to the intervention has on the treatment effect i.e. an estimate of the treatment effect amongst compliant patients. Descriptive statistics will be presented for the primary outcome in the control group, and in the intervention group split by the number of Sleepio sessions attended (i.e. 0,1,2,3, 4, 5, 6).

Baseline characteristic of the participants by compliance status will be reported. Statistical testing of baseline characteristics with compliance will be carried out to determine factors associated with compliance. A table of baseline characteristics by control, complier and non-complier with statistical comparison between compliers and non-compliers in the CBT-I intervention arm will be reported.

To obtain an unbiased estimate of the effect of compliance to the intervention on treatment effect, we will produce the complier-average causal effect estimates of the difference between the mean accuracy scores for sad and happy faces (FERT) for the compliers in the Sleepio group compared to the would be

compliers in the control group (CACE). For the primary CACE analysis, a sufficient level of adherence will be defined as completing at least 3 Sleepio sessions. The analysis will be performed using a two stage residual inclusion regression with randomisation as an IV. In the first stage, a regression of treatment receipt on randomisation will be conducted. In the second stage, a regression of the outcome on treatment receipt will be conducted, adjusting for the first-stage residual as covariates, as well as the same covariates as the intention-to-treat analysis. Bootstrapping will be used to obtain CI due to the two stage approach.

Exploratory analysis

Exploratory analyses will be conducted to assess the effect of dCBT-I on other expressions in the FERT (fear, anger, disgust, surprise, neutral), including the grouping of positive (happy, surprise) vs negative (fear, anger, disgust) expressions. We will also report and conduct exploratory analyses on reaction times and emotion misclassifications from the FERT. Emotion Misclassification is defined as the percentage of misclassifications for each emotion (Number of responses to each emotion when that emotion not displayed/Number of faces of all other expressions). Emotion reaction time is the calculated mean reaction time for correct responses for each emotion (if no correct responses, recorded as a missing value).

For the secondary objective tasks (ECAT, EMEM), we will further report and analyse % accuracy and % of misses (ECAT) and misclassifications of each condition (positive or negative words) and mean reaction time for correct responses for each condition (positive and negative words) (EMEM).

We will report sleep diary data collected as part of the dCBT-I treatment (in the intervention group) and also report % of participants scoring < 11 on the ISI and < 10 on the PHQ-9 after treatment, to provide a clinical context.

Possible predictors of treatment effects on the FERT will be analysed and reported. Specifically, we will investigate early/late chronotype, self-rated emotion regulation, high vs low depression scores (PHQ-9 dichotomised at 15) and worry as predictors of responses. Moderators will be assessed separately by repeating the primary analysis model and including an interaction term between randomised treatment and the moderator.

Sensitivity analysis

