The aim of the present study is to test if dCBT-I modifies emotional processing, including both objective measures of affective bias and self-report measures of emotional regulation, worry, perseverative negative thinking, mood and chronotype in patients with insomnia and comorbid depressive symptoms. Furthermore, it aims to examine if changes in emotional bias and/or emotional regulation mediate the effect of CBT-I on depressive symptoms. The protocol is modified compared to our previous study (described below) to enhance treatment adherence through increased contact with the study team and to extend the emotional test battery to include tests of emotional perception, categorization and memory.

The **primary** hypothesis for the trial is:

- dCBT-I will improve objective biases in negative emotional processing of faces relative to Sleep Hygiene Education (SHE) (5 and 10 weeks post randomisation)
 - a. Reduced recognition accuracy in response to sad facial expressions in the Facial Emotional Recognition Task (FERT)
 - b. Increased recognition accuracy in response to happy facial expressions in the FERT

The **secondary** hypotheses are:

- 1. dCBT-I will improve objective negative biases in categorization of emotional self-descriptors (5 and 10 weeks post randomisation) relative to SHE.
 - 1. Decreased reaction time to identify positive compared with negative characteristics in Emotional Categorisation Task (ECAT)
- 2. dCBT-I will increase positive emotional memory bias relative to SHE (10 weeks post randomisation)
 - 1. Increased memory for positive compared with negative words in the Emotional Memory Task (EMEM)
- 3. dCBT-I will reduce self-reported emotion regulation deficits (Difficulty with Emotion Regulation Scale, DERS), worry (Penn State Worry Questionnaire, PSWQ) and perseverative thinking (Perseverative Thinking Questionnaire, PTQ) (5 and 10 weeks post randomisation) relative to SHE.
- 4. dCBT-I will reduce self-reported depression severity (Patient Health Questionnaire, PHQ-9) (5 and 10 weeks post randomisation) relative to SHE.
- 5. dCBT-I will reduce insomnia severity (Insomnia Severity Index, ISI) (5 and 10 weeks post randomisation) relative to SHE.
- 6. Change in emotional perception of faces (FERT: Changes in recognition accuracy for happy and sad facial expressions) at week 5 will mediate change in depressive symptoms (PHQ-9) at week 10.

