Appendix 5k)			
ECAT	X	X	X
EMEM	X	X	X
Audit of engagement		Х	Х
with mental health			
services and sleep			
medication			
(Appendix 5i)			
Device Monitoring	X	X	X
Question(s)			
(Appendix 5a)			

Fig 2: Standard Protocol Items: Recommendations for Interventional Trials (SPIRIT) figure.

Randomisation and allocation concealment

Randomization will be performed independently from the study team through the ePRO system. This study will use stratified randomisation with an allocation ratio of 1:1, as recommended for small scale clinical trials (Kernan et al., 1999). Randomisation and stratification according to sex (male/female), age (25-44, 45-65), depression severity (PHQ-9 Scores: $\leq 15: \geq 16$) and insomnia severity (ISI scores $\leq 19: \geq 20$). On completion of baseline measures each participant will be randomly assigned to either dCBT-I or SHE. The team will be unable to influence randomization in the ePRO system, but will manually contact the participant to inform them of their allocation.

Blinding and bias

Self-report assessments and performance tasks will be completed entirely online. Participants will be informed of their randomisation outcome (dCBT-I or SHE, referred to as sleep treatment 1 and 2 in the PIS) and will not be blind to treatment allocation. To minimise bias, the PIS will not explicitly reveal that SHE is used as a minimal control.

End of study

The end of study is defined as the last participants completed the last assessment (10 weeks).

Sample size calculation

Our planned primary intention-to-treat analysis will compare dCBT-I versus SHE for objective biases in negative emotional processing of faces at week 10. Our desired sample size of n=200 and an estimated attrition rate of 20% (based on recently completed trials (Kyle et al., 2017)), will be powered to detect a minimum between group standardized effect size of 0.5 at week 10, with a power of 90% and a two-tailed α of 0.05.

Recruitment and payment

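### The SAP's 85% power is correct for each primary outcome taken singly but is worded as if for the pair; label it so, test the two by Holm, and align the protocol's primary time point

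*Combined protocol and SAP*

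**What the plan says.** SAP, Sample size calculation: 200 participants, 15% attrition, standardised difference 0.5 at week 10, first at two-sided 0.05 with 90% power. The section then says: "Considering the co-primary outcome, alpha will be adjusted to 0.025 to control the overall type 1 error rate". It assumes zero correlation between the outcomes, calls that assumption conservative, and concludes that "the study would be able to detect an effect size of 0.5 with 85% power on the two primary outcomes". On losses it adds: "The sample size remains inflated to allow for a rate of by 15% lost to follow up".

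SAP, Multiple comparisons and multiplicity: "Due to the use of 2 primary outcomes (accuracy for sad and happy faces, respectively) 0.05/2 = 0.025 will be considered significant". The same paragraph sends the reader to the protocol for the definition of the primary outcome. SAP, Primary analysis, plans two-sided 97.5% confidence intervals. The SAP's primary hypothesis covers week 10 only; week 5 accuracy is secondary.

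The protocol's primary hypothesis is wider: "dCBT-I will improve objective biases in negative emotional processing of faces relative to Sleep Hygiene Education (SHE) (5 and 10 weeks post randomisation"), with sad and happy accuracy as parts (a) and (b). The protocol's own Sample size calculation names week 10 alone, at alpha 0.05 without a split, and assumes 20% attrition.

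Neither document says in words how the two results combine if only one is significant.

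**The concern.** The power sentence does not say whether 85% applies to each outcome, to both or to at least one. Correlation between the outcomes has no bearing on the power of a single test, so naming it beside the power figure invites the reader to think of the pair. Someone who takes 85% as the chance of confirming both parts of the primary hypothesis would be about 14 points too optimistic.

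A fixed Bonferroni split also keeps the second test at 0.025 after the first has been rejected, when a step-down procedure with the same family-wise protection would test it at 0.05.

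Finally, the SAP points to the protocol for the primary outcome, and the protocol's primary hypothesis includes a week that the SAP treats as secondary. A reader working from the protocol would count four primary comparisons; one working from the SAP would count two.

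**Working it through.** **Inputs.** 200 randomised, 1:1 allocation, 15% loss, difference 0.5 SD, two-sided alpha 0.025 per outcome, zero correlation: all from the SAP. The calculation is an unadjusted two-group comparison, and the effect is taken as 0.5 on each outcome.

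**1. Starting calculation.** For 90% power at 0.05, n per arm = 2(1.960 + 1.282)²/0.5² = 84.1, rounded up to 85. Total 170, and 170/0.85 = 200. The SAP's starting figure reproduces.

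**2. The 85%.** Noncentrality = 0.5 × √(85/2) = 3.260. The critical value at two-sided 0.025 is 2.241. Power = Φ(3.260 − 2.241) = Φ(1.018) = 84.6%; noncentral t gives 84.0%. This is power for **one** outcome, and it agrees with the SAP's 85%.

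**3. The pair, zero correlation.**
- Both: p² = 0.8457² = 71.5% (t: 0.8398² = 70.5%).
- At least one: 1 − (1 − p)² = 97.6% (t: 97.4%).

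**4. Sensitivity to correlation.** The documents give no value beyond the assumed zero. Take the correlation between the two test statistics, each signed in its favourable direction, over an assumed range of −0.5 to 0.8. By the bivariate normal, power for both runs from 69.5% to 78.6%, and for at least one from 99.7% down to 90.6%.

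**5. Error control of the SAP's rule.** Two independent tests at 0.025: 1 − 0.975² = 4.94%. Correlation of either sign lowers it (4.84% at ±0.3, 4.65% at ±0.5, 4.02% at ±0.8). The rule is valid, and zero correlation is its worst case.

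**6. Holm instead of the fixed split.** Test the smaller p-value at 0.025; if it is rejected, test the other at 0.05. By noncentral t, single-test power is 0.8999 at 0.05 and 0.8398 at 0.025, a difference of 0.0601. Under independence:
- A given outcome: 0.8398 + 0.0601 × 0.8398 = 89.0%.
- Both: 0.8999² − 0.0601² = 80.6%.
- At least one: unchanged, since the first step is the same.

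| Power (85 per arm, 0.5 on each) | Fixed 0.025 each | Holm |
|---|---|---|
| A given outcome | 84.0% | 89.0% |
| Both | 70.5% | 80.6% |
| At least one | 97.4% | 97.4% |

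The gain needs an effect on both outcomes. If the other outcome has none, power for a given outcome is 0.8398 + 0.0601 × 0.025 = 84.1%, so little is gained and nothing is lost.

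**7. Attrition as in the protocol.** With 20% loss (80 per arm) and the fixed split, the normal approximation gives 82.1% per outcome, 67.5% for both and 96.8% for at least one.

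**The case against.** The strongest defence is that nothing is miscalculated. The 85% is the right marginal power for a Bonferroni pair. Coming straight after a per-test alpha, the phrase can be read as meaning each of the two outcomes. This stands.

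The SAP taken alone also gives a complete and valid testing rule: two named outcomes, one primary time point, 0.025 each, matching 97.5% intervals, week 5 secondary, family-wise error at most 5%. This stands too. A reader might infer from the co-primary label that the plan has no coherent decision rule; the SAP's multiplicity and primary analysis sections do not support that.

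A reader might say that zero correlation matters only for joint power, and is not conservative there because sad accuracy is meant to fall while happy accuracy rises. But correlation also sets the family-wise error, which is the subject of the sentence before, and there zero is the worst case. For joint power the effect is small: 71.5% at zero against 70.1% at −0.3, both normal approximation.

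A reader might also count four primary tests at 0.025 and reach 1 − 0.975⁴ = 9.6%. That joins the protocol's hypothesis wording to the SAP's alpha, which neither document plans, and treats two visits by the same participants as independent.

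The planned model adjusts for baseline, so true power may be higher. If 0.5 is on the unadjusted scale and the baseline-to-follow-up correlation is 0.3 to 0.5 (an assumption), power is roughly 87–93% per outcome and 77–87% for both. This shifts the levels but leaves the gap between per-outcome and joint power.

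Last, Bonferroni is an acceptable choice and fits the planned intervals. That is fair; the case for Holm is that it never rejects less at the same error rate.

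**Conclusion.** This is a cheap improvement, not an error that threatens the trial. The 85% is correct per outcome and ambiguous as worded. The figures missing beside it are about 71% for both and about 97% for at least one, given 85 per arm, 0.5 on each outcome, an unadjusted comparison and the SAP's zero correlation.

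It would go too far to say that the trial has only 71% power for its primary objective: no section requires both outcomes to be significant. If both were required, no split would be needed, and testing each at 0.05 would give 0.8999² = 81.0%.

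Replacing the fixed split by Holm gains about 5 points per outcome (84.0% to 89.0%) and about 10 points for both (70.5% to 80.6%), if both effects are real and the tests independent, with family-wise error still at most 5%. The difference in primary time point between the protocol's hypothesis and the SAP is a discrepancy to reconcile; it does not enlarge the SAP's primary family.

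**What to change.** 1. In the SAP's Sample size calculation, state that the 85% is power for each outcome at two-sided 0.025, and add about 71% for both and about 97% for at least one under zero correlation.
2. State that sad and happy accuracy at week 10 are two separate primary claims, so that a mixed result has an agreed reading. Test them by Holm: smaller p-value against 0.025 and, if rejected, the other against 0.05.
3. Amend the protocol's primary hypothesis to week 10, as in the SAP and the protocol's own sample size section. The attrition rate (20% in the protocol, 15% in the SAP, from the same cited source) can be reconciled at the same time.

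The cost is some SAP wording and a one-line protocol amendment, made before any comparison by arm is seen. No participants or data are added. The one downside is that the 97.5% interval for the second outcome may include zero when Holm rejects it at 0.05; the SAP should say that these intervals are then descriptive.
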